11.0 Data Collection and Analysis

11.1 Data Collection

Data from screening, surveys and phone communications will be collected by operators and input directly into the Mayo Clinic Electronic Data Capture (Redcap) system.

11.2 Data Analysis

Table 5 below details how data from the surveys will be analyzed.

Table 5: Details of how measurements will be analyzed

Measurement	General details on purpose of analysis	Specific details on analysis
Participant perspective surveys	Feeding system surveys at baseline and end of study, to assess participant perspectives on feeding system specific parameters and the impact of converting from usual system(s) to Mobility+	Surveys consist of 16 five-point Likert scale type questions, where rating options either range from very difficult to very easy, or strongly disagree to strongly agree. The ratings are assigned a point scoring system, whereby the most negative option (i.e. very difficult or strongly disagree) is assigned 0 points and the most positive option (i.e. very easy or strongly agree) is assigned 4, meaning the total possible maximum score is 64 points. As participants are asked to complete these surveys at baseline and at study end, the overall score obtained with their usual systems can be compared to the overall score obtained after using Mobility+. Scores for individual questions can also be compared.
QoL measures (QoL survey at baseline and QoL question at end of study)	A simple QoL measure will be used at baseline to gauge participants overall QoL using a scale previously published (See Appendix 5) accompanied by a simple question evaluating if self-perceived QoL has changed, at end of study	Determine baseline QoL Evaluate any changes to QoL in the second week of study

General End of Study Questions	
This survey is designed to assess changes in participants perceived wellbeing and mobility from study start – where they used their usual feeding system – to study end with Mobility+. It will also capture additional information on Mobility+ usage patterns and consumer demand for Mobility+.
	
The survey consists of 9 simple questions which predominantly assess change in participants perceived wellbeing and mobility with Mobility+ versus their usual systems. The questions are mostly Likert scale type questions where answer options range from “much better” to “much worse”. Additional questions assess the importance of mobility to the participant, how the participant wore the Mobility+ and if the participant would like to use the Mobility+ again, among others. Data collected will supplement QoL and participant perspectives data.

---------------------------------------	---	--

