3.0 Purpose

The purpose is to evaluate the safety and effectiveness of Mobility+ enteral feeding system via this initial post-market study (510k clearance number K222678) in adults, a subset of the intended use population. This evaluation will be conducted in a prospective, single arm, non-randomized clinical study.

Hypothesis and Objectives

The study hypothesis is that Mobility+ meets its intended use, safely. The objectives are to evaluate the below primary and secondary endpoints, through execution of this protocol:

Endpoint	Detail	How it will be measured
Primary: Safety and Effectiveness of Mobility+	Evaluate participants who have received familiarization training can use device, according to IFU, to allow delivery of liquid nutrition to their feeding tube, in a real-life setting (home), safely (i.e. can execute critical device use tasks to allow feeding, without serious adverse events) and with effectiveness (i.e. using Mobility+ for the majority or all of their feeding sessions i.e. two daily feeds, minimum)	Phone communication and checklist (Appendix8)

Secondary: Usability of Mobility+	Evaluate Participant perspectives on mobility, ease of use and tolerance, with their current feeding system(s) and Mobility+	Participant perspectives surveys: Baseline (Appendix 4) End of study (Appendix 7)
	Evaluate changes in participant Quality of Life (QoL)	QoL survey at baseline (Appendix 5) and QoL question at end of study (Appendix 7)
	Estimate if participants consume similar average volume (and kcals) of feed/day during the study, compared to baseline	Collect descriptive data on estimated average feed volume and kcals consumed at baseline (Appendix 3) and at end of study (Appendix 8)

The outcome will be presented in a study report.

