Which type of feeding tube do you have?	G-tube 	J-tube 

Appendix 4
Participant perspectives baseline survey

 Participant perspectives of current feeding system: Usability, mobility and ease of use

(Operator asks the Participant these questions)

During use of your current feeding system, how do you find these activities?	Very Difficult	Difficult	Neutral	Easy	Very Easy	
Moving from one room to another room						
Going up and down stairs						
Short walk (e.g., one block)						
Long walk (e.g., several blocks)						
Travelling in car/public transport						
Moderate intensity physical activities, such as: - Moving a table - Pushing a vacuum - Bowling - Playing golf						
Other daily activities (e.g., lifting or carrying groceries, household chores)						
Ability to sleep						
Socializing with friends/family						
During use of your current feeding system, how do you find working/studying or both? Please log as N/A if participant does neither.	Very Difficult	Difficult	Neutral	Easy	Very Easy	N/A
Note to operator: When scoring this questionnaire, assign points using the legend below. Very Difficult = 0 points, Somewhat Difficult = 1, Neutral = 2, Somewhat Easy = 3 and Very Easy = 4						
Thinking about your overall experience with your current system, how strongly do you	Strongly Disagree	Some-what Disagree	Neutral	Some-what Agree	Strongly Agree	

agree or disagree with the following statements?					
My current system is easy to use					
My current system is easy to carry					
The noise level of my current system during use (including alarms) is acceptable					
My current system allows me to feed discreetly					
I am satisfied with the overall performance of my current system					
Note to operator: When scoring this questionnaire, assign points using the legend below. Strongly Disagree = 0 points, Somewhat Disagree = 1, Neutral = 2, Somewhat Agree = 3 and Strongly Agree = 4					
Do you experience any of the following symptoms of feed intolerance while using your current feeding system?					
Gas/Bloating?	 Yes			 No	
If yes, is it mild, moderate, or severe?	 Mild	 Moderate	 Severe		
Abdominal Pain?	 Yes			 No	

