Trial Day 5: SKU that participant is using: 
 
 440mm RED 	700mm BLUE 	1000mm GREEN 	1900mm WHITE 	
 
					440mm RED 	700mm BLUE 	1000mm GREEN 	1900mm WHITE 
440mm RED 	700mm BLUE 	1000mm GREEN 	1900mm WHITE 					
Select one: 		Stay on this SKU 						
		Trial _____ SKU 						
Reason for changing: <hr/>								
Have you been admitted to hospital in the last 5 days/during this trial period?		 Yes		 No				
Note to operator: Confirm you have reminded participant of the day they will begin the 14 day study period		 Yes		 No				

Appendix 7

Participant perspectives outcome survey

Participant perspectives of Mobility+ feeding system: Usability, mobility, and ease of use, including general end of study questions

(Operator asks the Participant these questions)

During use of the Mobility+ system, how do you find these activities?		Very Difficult	Difficult	Neutral	Easy	Very Easy
Moving from one room to another room						
Going up and down stairs						
Short walk (e.g., one block)						
Long walk (e.g., several blocks)						
Travelling in car/public transport						
Moderate intensity physical activities, such as:						

 - Moving a table - Pushing a vacuum - Bowling - Playing golf 						
Other daily activities (e.g., lifting or carrying groceries, household chores)						
Ability to sleep						
Socializing with friends/family						
During use of the Mobility+ system, how did you find working/studying or both? Please log N/A if participant does neither	Very Difficult	Difficult	Neutral	Easy	Very Easy	N/A
Note to operator: When scoring this questionnaire, assign points using the legend below.						
Very Difficult = 0 points, Somewhat Difficult = 1, Neutral = 2, Somewhat Easy = 3 and Very Easy = 4						
Thinking about your overall						

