experience with the Mobility+ system, how strongly do you agree or disagree with the following statements?	Strongly Disagree	Some-what Disagree	Neutral	Some-what Agree	Strongly Agree
The Mobility+ system is easy to use					
The Mobility+ system is easy to carry					
The silent nature of The Mobility+ system during use is acceptable					
The Mobility+ allows me to feed discreetly					
I am satisfied with the overall performance of the Mobility+ system					
Note to operator: When scoring this questionnaire, assign points using the legend below. Strongly Disagree = 0 points, Somewhat Disagree = 1, Neutral = 2, Somewhat Agree = 3 and Strongly Agree = 4					
Do you experience any of the following symptoms of feed intolerance while on your current feeding system?					
Gas/Bloating?	□ Yes			□ No	
If yes, is it mild, moderate, or severe?	Mild □	Moderate □	Severe □		
Abdominal Pain?	□ Yes			□ No	
If yes, is it mild, moderate, or severe?	Mild □	Moderate □	Severe □		
Diarrhea?	□ Yes			□ No	
If yes, is it mild, moderate, or severe?	Mild □	Moderate □	Severe □		
Constipation?	□ Yes			□ No	
If yes, is it mild, moderate, or severe?	Mild □	Moderate □	Severe □		
Nausea/Vomiting?	□ Yes			□ No	
If yes, is it mild, moderate, or severe?	Mild □	Moderate □	Severe □		
Reflux?	□ Yes			□ No	
If yes, is it mild, moderate, or severe?	Mild □	Moderate □	Severe □		
Have you been admitted to hospital since you last received phone communication?	□ Yes			□ No	
General End of Study Questions:					

When answering the following questions, consider how **the last 14 days with Mobility+** have been compared to an average week of using the feeding system that you had **before you started this study**. Please try to answer based **solely on your experience with the Mobility+** in the last two weeks and not on external factors that may have positively/negatively impacted your week of using the Mobility+.

How do you feel your overall Quality of Life has been during the last 2 weeks of using Mobility+?

Excellent	Good	Neutral	Bad	Very Bad
				

How mobile have you been in your everyday activities during the last 2 weeks of using Mobility+, compared to before you started the study?

Much Better	Somewhat Better	About the Same	Somewhat Worse	Much Worse
				

How do you rate the importance of being mobile in your everyday activities to your overall wellbeing?

Very Important	Somewhat important	Not important at all

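### The perspectives score is defined as 16 items and 64 points, but the forms hold 15 items and 60; the SAP scores it differently, with no rule for N/A and no stated purpose for the ANOVA

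*Protocol*

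**What the plan says.** Protocol section 3.0 makes the survey the measure of a secondary endpoint: "Evaluate Participant perspectives on mobility, ease of use and tolerance, with their current feeding system(s) and Mobility". Section 11.2, Table 5, defines the score. It states "Surveys consist of 16 five-point Likert scale type questions", gives 0 points to the most negative answer and 4 to the most positive, and concludes "meaning the total possible maximum score is 64 points". It then compares the overall score on the usual system with the overall score on Mobility+, and allows single questions to be compared as well.

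The baseline form (Appendix 4) and the outcome form (Appendix 7) print a matching legend: "Very Difficult = 0 points, Somewhat Difficult = 1, Neutral = 2, Somewhat Easy = 3 and Very Easy = 4", with 0 to 4 again for the agreement items. Both let the work/study item go unanswered. At baseline the instruction is "Please log as N/A if participant does neither"; at outcome it is "Please log N/A if participant does neither".

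SAP section 4.0 scores every rating from 1 to 5 under three measures: mobility (easy/difficult answers), ease of use (agree/disagree answers) and quality of life. An overall score per measure is formed and then averaged over the cohort. SAP section 5.0 names a paired t-test together with ANOVA, at a significance level of 0.05. SAP section 6.0 reports that 11 of 17 participants (64.7%) were neither working nor studying.

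**The concern.** A score for a named secondary endpoint should have one item list, one scale, one way of combining items and one rule for items that do not apply. Here the stated item count does not match the forms. The SAP also moves, without comment, from a single 0 to 4 total to separate 1 to 5 scores. Neither document says whether a participant's items are summed or averaged, or what an N/A is worth, although the work/study item does not apply to most of the cohort.

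What is at stake is whether a reader can tell what range a reported score lies on, which items it contains, and how many participants stand behind the comparison of Mobility+ with the usual system.

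**Working it through.** **1. The stated maximum.** 16 items × 4 points = 64, so Table 5's multiplication is right. The item count is the input to check.

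**2. Counting the forms.** Both forms list the same items in the same order:
- 9 activity items: moving between rooms, stairs, short walk, long walk, travel, moderate activity, other daily activities, sleep, socializing.
- 1 work/study item, with N/A allowed.
- 5 agreement items: easy to use, easy to carry, noise, discreet feeding, overall satisfaction.

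9 + 1 + 5 = 15 items, and 15 × 4 = 60. If work/study is N/A and adds nothing, 14 × 4 = 56.

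**3. Looking for a sixteenth item.** None qualifies on both forms.
- The quality of life question uses a scale from excellent to very bad, which Table 5 does not include in this score, and it has its own row there.
- The question on wanting to use the device again appears at outcome only, and Table 5 treats it among the general end-of-study questions.
- The intolerance questions are yes/no with a severity grade.
- The bullets under moderate activity are examples within one item.

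**4. The two scoring systems.** The split by measure assumes that the SAP's response scales sort the items.

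| Score | Items | 0 to 4 sum | 1 to 5 sum |
|---|---|---|---|
| Total | 15 | 0 to 60 | 15 to 75 |
| Mobility with work/study | 10 | 0 to 40 | 10 to 50 |
| Mobility without work/study | 9 | 0 to 36 | 9 to 45 |
| Ease of use | 5 | 0 to 20 | 5 to 25 |

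If the SAP score is a mean of items, each range is 1 to 5.

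**5. Effect of the scale shift alone.** Moving to 1 to 5 adds 1 to every item at both visits. With k items answered at both, the change is (outcome sum + k) − (baseline sum + k) = outcome sum − baseline sum. The paired test is unchanged. In simulated complete data (17 participants, 15 items), t was −0.423 on both scales.

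**6. Effect of the N/A rule.** Of the 17 participants, 11 neither worked nor studied (11/17 = 64.7%). Three unstated rules are possible:
- *N/A counts as zero.* On 0 to 4 this equals Very difficult; on 1 to 5 it lies 1 point below it. If N/A is logged at both visits, the item adds nothing to the change in the sum.
- *N/A is averaged over.* The participant's mobility mean rests on 9 items instead of 10. With complete items, a sum and a mean differ by one constant factor and give the same t. With N/A present the divisor is 9 for some participants and 10 for others, so sum and mean no longer give the same test.
- *All items required.* Up to 11 participants leave the total and the mobility score: 17 − 11 = 6 remain. Ease of use is unaffected, because work/study is not among its items.

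**7. The ANOVA.** With two time points and no other factor, repeated-measures ANOVA gives F = t². In the same simulated data F = 0.1789 and (−0.42297)² = 0.1789. It therefore repeats the paired t-test unless a further factor is meant, and the SAP names none.

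**The case against.** The strongest reply is that this is a documentation error in a secondary usability survey. The primary endpoint does not use the score, the scale shift leaves a paired test untouched, and an N/A scored as zero at both visits drops out of the change in a sum. A reader might also infer from the gaps that the score cannot be reconstructed at all. That goes too far: the SAP prints the answer options for each measure, and these correspond to the two blocks on the forms, so membership can reasonably be guessed (10 mobility items, 5 ease-of-use items). Likewise, it is literally true that the test is not tied to an endpoint. But SAP section 5.0 follows directly on the three scored measures, and a paired test of those scores is the natural reading. Only the ANOVA is unexplained.

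These points limit the weight of the finding. They do not remove the wrong count, the unacknowledged change of scoring, or the missing N/A rule. Nor can one conclude that N/A matters only for someone whose status changes between visits, since a complete-item rule could remove most of the cohort.

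Two further inferences are tempting. The noise item reads "The noise level of my current system during use (including alarms) is acceptable" at baseline and "The silent nature of The Mobility+ system during use is acceptable" at outcome, which might suggest a comparison tilted by wording; the documents give no evidence of such an effect or its size, and adapting the item to a silent device is a defensible choice. One might also suppose that the outcome-only question on using the device again was counted to reach 16; Table 5's own layout speaks against that.

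**Conclusion.** The point stands as a matter of definition and reproducibility. The count and maximum in Table 5 are wrong against the forms by 1 item and 4 points (15 and 60 against 16 and 64). The protocol and SAP use different scales and different scoring units, and the SAP does not say that it departs from the protocol. The change of scale affects reported levels only; replacing one total by separate measures changes what is compared. The N/A rule is the part that can alter a result, with between 6 and 17 participants contributing to the total or the mobility score, depending on the rule.

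This rests on three assumptions: that no row is missing from the text of both forms (unlikely, as both show the same 15 items in parallel); that the answer scales define the SAP's measures; and, for the figure of 6, that all 11 participants who neither worked nor studied were logged as N/A. SAP section 6.0 reports occupation at enrollment, not survey answers. A reader might infer that the reported comparison is biased. The documents show no survey scores and do not say which N/A rule was used, so neither a bias nor its absence can be established. The correction should be made, but it does not bear on the primary endpoint.

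**What to change.** 1. Correct Table 5 to 15 items and 60 points. If an item was dropped from the forms, say so instead.
2. Use one scale and one scoring unit in both documents. Because the SAP is written in the past tense, a deviation note recording its departure from Table 5 would also serve.
3. List the items in each measure: the 10 easy/difficult items, including work/study, under mobility; the 5 agreement items under ease of use.
4. Score each of these two measures as the participant's mean of items answered at both visits, so that an N/A neither counts as zero nor removes the participant. Other rules are defensible; the essential step is to state one.
5. Report the paired t-test with a 95% CI for each measure. State the endpoint and factor of the ANOVA, or remove it if none was run.
6. Label any rescoring post hoc and show it beside the scores already calculated.

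The cost is wording in Table 5 and SAP sections 4.0 and 5.0 (or a deviation note), a small rescoring effort, and the post hoc label on any rescored result. No new data are needed.

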12.0 Data management

A validated Electronic Data Capture system will be used at the study site, which complies with all relevant local and national rules.

13.0 Maintain Records

Records shall be maintained in accordance with SOP002 Control of Records Procedure.

14.0 Appendices

Appendix 1

Eligibility-Screening Log

Date:		
Operator(s) ID:		
Questions:	Answers:	
All answers to the following questions must be 'YES' for a candidate to be deemed eligible for this Study.		
1. Is the candidate at least 18 years of age?	YES 	NO 
2. Do they have a gastrostomy tube or jejunostomy tube?	YES 	NO 
3. Do they use a standard enteral feeding system (gravity bag, enteral nutrition pump, bolus or combination(s)?	YES 	NO 
4. Have they been on an enteral feeding regime for greater than or equal to 10 weeks?	YES 	NO 
5. Do they currently require greater than or equal to 500ml enteral nutrition every day ?	YES 	NO 
6. Do they tube feed either during the day or day and night ?	YES 	NO 
7. Is their clinical functional capacity adequate to enable them to participate fully in the study? (Determined by operator clinical judgement)	YES 	NO 
8. Is the patient mobile? (Determined by operator clinical opinion)	YES 	NO 
9. Do they currently use a commercially available enteral formula that is listed on the Mobility+ Flow Rate Guide?	YES 	NO 

Appendix 2
Screening Questionnaire

(Operator asks the Participant these questions)

Participant ID:						
Date:						
Operator(s) ID:						
Questions:	Answers:					
1. What type of feeding system(s) do you use?	GRAVITY BAG 	PUMP 	SYRINGE/BOLUS 	COMBINATION 		
If COMBINATION, please give detail						
2. What is the name of the enteral feed you use?	Brand:		Type:			
3. Do you feed during the day, at night or a combination of both?	DAY 	NIGHT 	COMBINATION 			
4. What volume (and kcals) of enteral nutrition do you typically consume over a 24 hour period? mls	 kcals			
5. How many feeding sessions do you have per day?					
6. How many hours do you typically infuse for over a 24 hour period? hours	 minutes			
7. What flow rate do you typically use (i.e. per feeding, what ml of formula do you provide over how many minutes)?	0-50ml/hr 	50-100ml/hr 	100-150ml/hr 	UNSURE* 		
*Calculated Average Flow Rate:						
8. How many full feeding sessions do you miss a day?	0	1	2	3	4	Other
9. How many feeding sessions do you cut short each day?	0	1	2	3	4	Other
10. Are you able to swap from your current system to Mobility+ for a minimum of two daily feeds (operator calculates this volume using	YES 		NO 			

answer to Q.4 and Q.5) for a trial period of 5 -7 days, followed by 14 consecutive study days? *Note to operator: minimum device fill is 250ml (as per precautions in IFU)			
Operator Facing Questions			
11. Is the subject a suitable candidate for using Mobility+ based on their enteral feeding needs and alignment to the Mobility+ Flow Rate Guide (See giving set SKU decision tree for prescribing Mobility+ Figure 6)	YES 	NO 	
The candidates feed and flow rate needs mean the most appropriate tubing SKU to start them on during trial days is:			
440mm RED 	700mm BLUE 	1000mm GREEN 	1900mm WHITE 

Appendix 3
Demographics questionnaire

(Operator asks the Participant these questions where these elements are not already captured from Electronic Medical Records)

Questions:	Answers:	
Are you male/female?	Male 	Female 
What is your age? (years)	
What is your height (cm)? cm	
What is your weight (kg)? kg	
What is your diagnosis? Note: Operator selects a standard pathophysiological mechanism from list	 Malignancy  Mechanical Obstruction  GI Dysmotility  Hepato-biliary/Pancreatic  Mucosal Disease  Trauma/Injury  Neuro-degenerative Disease  Short Bowel Syndrome  Functional Disorder  Bariatric Surgery  Congenital/Developmental	
Are you working or studying (or both)?	Yes, I work, study or both 	No, I neither work or study 
Which type of feeding tube do you have?	G-tube 	J-tube 

Appendix 4
Participant perspectives baseline survey

 Participant perspectives of current feeding system: Usability, mobility and ease of use

(Operator asks the Participant these questions)

During use of your current feeding system, how do you find these activities?	Very Difficult	Difficult	Neutral	Easy	Very Easy	
Moving from one room to another room						
Going up and down stairs						
Short walk (e.g., one block)						
Long walk (e.g., several blocks)						
Travelling in car/public transport						
Moderate intensity physical activities, such as: - Moving a table - Pushing a vacuum - Bowling - Playing golf						
Other daily activities (e.g., lifting or carrying groceries, household chores)						
Ability to sleep						
Socializing with friends/family						
During use of your current feeding system, how do you find working/studying or both? Please log as N/A if participant does neither.	Very Difficult	Difficult	Neutral	Easy	Very Easy	N/A
Note to operator: When scoring this questionnaire, assign points using the legend below. Very Difficult = 0 points, Somewhat Difficult = 1, Neutral = 2, Somewhat Easy = 3 and Very Easy = 4						
Thinking about your overall experience with your current system, how strongly do you	Strongly Disagree	Some-what Disagree	Neutral	Some-what Agree	Strongly Agree	

agree or disagree with the following statements?					
My current system is easy to use					
My current system is easy to carry					
The noise level of my current system during use (including alarms) is acceptable					
My current system allows me to feed discreetly					
I am satisfied with the overall performance of my current system					
Note to operator: When scoring this questionnaire, assign points using the legend below. Strongly Disagree = 0 points, Somewhat Disagree = 1, Neutral = 2, Somewhat Agree = 3 and Strongly Agree = 4					
Do you experience any of the following symptoms of feed intolerance while using your current feeding system?					
Gas/Bloating?	 Yes			 No	
If yes, is it mild, moderate, or severe?	 Mild	 Moderate	 Severe		
Abdominal Pain?	 Yes			 No	
If yes, is it mild, moderate, or severe?	 Mild	 Moderate	 Severe		
Diarrhea?	 Yes			 No	
If yes, is it mild, moderate, or severe?	 Mild	 Moderate	 Severe		
Constipation?	 Yes			 No	
If yes, is it mild, moderate, or severe?	 Mild	 Moderate	 Severe		
Nausea/Vomiting?	 Yes			 No	
If yes, is it mild, moderate, or severe?	 Mild	 Mild	 Mild		
Reflux?	 Yes			 No	
If yes, is it mild, moderate, or severe?	 Mild	 Mild	 Mild		

